# 4. EFFICACY, PHARMACOKINETIC AND PHARMACODYNAMIC ANALYSES

## 4.1 EFFICACY

All efficacy endpoints are secondary endpoints in this roll-over study and will be evaluated descriptively. Efficacy endpoints will be presented for the Roll-over set.

## 4.1.1 Available data

Efficacy data are collected by assessments of PDAI, DC, EoC, CR, CRmin, CRoff, cumulative prednisone dose, flares and treatment failure. Quality of life will be measured using Autoimmune Bullous Disease Quality of life (ABQOL) Questionnaire and EuroQoL 5-Dimension 5-Levels- (EQ-5D-5L) Scale. The health impact of glucocorticoid (GC) use will be measured using the Glucocorticoid Toxicity Index (GTI).

#### 4.1.2 Endpoints and derivation rules

For all references to visits, analysis visits are considered as described in section 2.2.4 unless specified otherwise. If multiple assessments fall within the same analysis window, only the assessment closest to the target date will be considered unless specified otherwise. Other assessments within this window will only be listed and not considered in the below analyses. Only the time to event endpoints will be derived using all possible measurements and not only the one closest to the target of the analysis visit.

#### 4.1.2.1 **PROPORTION OF PARTICIPANTS WHO ACHIEVE CRMIN AND CROFF**

The proportion of participants who achieve CRmin in 1905 (as assessed by the investigator) will be derived within each treatment period, within the follow-up phase and over the entire study (ie, whether the participant achieves the status during at least one treatment period or during the follow-up phase).

Missing values for the below reasons, will be imputed as follows:

- all CR assessments missing: CRmin = non-response
- CRmin never ticked: CRmin = non-response
- CRmin is ticked but date of CRmin is missing: date for CRmin will be imputed by disease assessment visit date

Proportions will be calculated overall and by subgroup of disease status at roll-over.

Similar analyses as described above for CRmin will be performed for CRoff.

For the roll-over phase of participants who enter study 1905 on CRmin, only the proportion of participants achieving CRoff will be derived, as participants already achieved CRmin before the start of 1905. Participants entering 1905 on CRoff will be excluded from this calculation.

For the follow-up phase, participants who start the follow-up phase on CRmin (or CRoff) will be excluded from this calculation.

SGS	Statistical Analysis Plan	
ARGX-113-1905	Final analysis	Final 1.0 of 26APR2024

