Follow-up		End of treatment phase + 1 minute		e of last contact, with 23:59 ed as time part.

a In case no 1905 ICF date is available, participant data will not be considered in the analysis

b Not applicable for participants who enter 1905 on CRmin. They will start immediately in Treatment period 2 of the Treatment phase in case of flare

A new treatment period is considered for participants with a flare after achieving CRmin (ie, while being off IMP treatment). A new treatment period is not considered after temporary IMP discontinuation for an adverse event. Repeat until the last on-treatment or off-treatment subperiod.

Participants who enter 1905 on CRmin, will not have a treatment period 1 in the treatment phase, but will start immediately with treatment period 2 at first IMP intake in 1905 (ie, after the first flare in 1905). Note: treatment period 2 is defined in 1905 as the treatment period starting after the first flare within 1905. Treatment given before a first flare in 1905 is considered belonging to treatment period 1.

Adverse events (AEs) and concomitant therapies will be allocated to phases and periods as described in sections 5.1.2 and 3.3.2 respectively. All other assessments will be allocated to phases (PDAI, PD, PK, albumin and LDL-C also to periods and subperiods) based on the assessment date(time).

In case of (partially) missing date(time) fields disabling allocation, information from the visit/timepoint label and protocol schedule of activities will be used to allocate to the correct phase, period and subperiod. If this is not possible (unscheduled visits or visits on a turning point between phases, periods or subperiods), assessments will be handled as follows:

- Treatment phase vs. roll-over phase: assessments will be allocated to the treatment phase unless the available parts of the assessments start or stop date/time provide evidence for allocating to the roll-over phase.
- Treatment phase vs. follow-up phase: assessments will be allocated to the treatment phase unless the available parts of the assessments start or stop date/time provide evidence for allocating to the follow-up phase.
- On-treatment vs. off-treatment subperiod within a treatment period: assessments will be allocated to the on-treatment subperiod unless the available parts of the assessments start or stop date/time provide evidence for allocating to the off-treatment subperiod.

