# 2.4.1 Calculation of descriptive statistics and percentages

For continuous parameters, full descriptive statistics will only be presented if there are at least 2 non-missing observations. Alternatively, only the number of non-missing data points and mean are shown.

Descriptive statistics will include the number of non-missing data points, the arithmetic mean, the standard deviation (SD), the standard error (SE), the median, minimum, first quartile (Q1), third quartile (Q3), and maximum.

Descriptive statistics for immunogenicity titer values will also include geometric mean (GM) and geometric standard deviation (GSD).

Mean, Q1, Q3, median, GM and GSD will be presented with 1 more decimal place than the measured values, with maximum 4 decimal places. SD and SE will be presented with 2 more decimal places than the measured values, with maximum 5 decimal places. Minimum and maximum will be presented with the same number of decimal places as the measured values, with maximum 3 decimal places.

SGS	Statistical Analysis Plan	
ARGX-113-1905	Final analysis	Final 1.0 of 26APR2024

Descriptive statistics of PK concentrations will include number of non-missing data points, arithmetic mean, SD, median, minimum and maximum, and the coefficient of variation (CV%). The descriptive statistics will be presented with 3 significant digits. If more than half of the values are BLQ, arithmetic mean will be set to BLQ and SD and CV% will not be calculated.

For event-type data, the denominator will be all participants in the analysis set per treatment and phase/period/subperiod (as applicable).

For frequency tabulations and cross-tabulations, the denominator will be all participants in the analysis set per treatment. For tables where results are shown by analysis visit, the denominator will be all participants in the analysis set per treatment and per analysis visit. Missing values will never be included in the denominator count when computing percentages. For cross-tabulations of post-baseline results versus baseline results, a 'missing' category will be shown for baseline results if applicable.

Percentages will be shown with one decimal place.

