### 4.1.3 Presentation of results

#### 4.1.3.1 **PROPORTION OF PARTICIPANTS WHO ACHIEVE CRMIN AND CROFF**

Frequency tabulations will be provided of the percentage (with 95% exact confidence interval) of PV participants and all participants (PV+ PF) achieving CRmin within each treatment period, within the follow-up phase and over the entire study. The table will be repeated by disease status at roll-over.

Similar tables will be provided for the percentage of participants achieving CRoff.

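### Under the SAP's written rules, participants who enter 1905 in CRmin or CRoff and never flare cannot count as overall CRmin achievers, yet stay in the pooled denominator

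*SAP*

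**What the plan says.** The CRmin proportion is the first-listed secondary efficacy endpoint (Protocol section 3), first for PV and then for PV and PF together. The SAP flags it as a topline table (section 8.1).

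- **Numerator.** Section 4.1.2.1 takes CRmin "over the entire study (ie, whether the participant achieves the status during at least one treatment period or during the follow-up phase". For the roll-over phase of participants who enter in CRmin, "only the proportion of participants achieving CRoff will be derived, as participants already achieved CRmin before the start of 1905". It adds: "For the follow-up phase, participants who start the follow-up phase on CRmin (or CRoff) will be excluded from this calculation". On missing data it states "CRmin never ticked: CRmin = non-response".
- **Treatment periods.** Section 2.2.1 says "Participants who enter 1905 on CRmin, will not have a treatment period 1 in the treatment phase". They go straight to period 2, and only if they flare and restart IMP. CRoff entrants are grouped with CRmin entrants (section 2.5, note 1).
- **Denominator.** Efficacy uses the Roll-over set (section 4.1). The general rule in section 2.4.1 is "For frequency tabulations and cross-tabulations, the denominator will be all participants in the analysis set per treatment". Section 4.1.3.1 asks for frequency tabulations of participants "achieving CRmin within each treatment period, within the follow-up phase and over the entire study", with exact 95% confidence intervals. It states no narrower denominator.
- **Overview table (section 4.1.3.7).** Footnote d defines Overall as including the roll-over phase where that applies. The cell for CRmin entrants in the overall CRmin row carries footnote a. The pooled Overall cell in that row does not.

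**The concern.** The rules for the numerator and the denominator do not fit together for one group. Someone who enters in remission and stays there for the whole study has the best course available, but the written rules give that person no route into the numerator while leaving them under the percentage. An entrant who flares, is retreated and regains CRmin can be credited. The pooled percentage then mixes two things: how often CRmin is reached by those who could still reach it, and how many participants arrived already having it.

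Results are shown by 1904 randomised arm (SAP section 2.1.2). If the arms delivered different shares of lasting remission into 1905, the pooled percentages would differ for that reason alone.

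**Working it through.** The plan states no rate, power or sample-size figure for this endpoint (Protocol sections 9.2 and 9.3), so there is no figure to reproduce. The check traces one participant through the rules and then sizes the effect.

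**1. Numerator for a CRmin or CRoff entrant who never flares**

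| Part of 1905 | SAP rule | Can CRmin count? |
|---|---|---|
| Roll-over phase | 4.1.2.1: only CRoff is derived | No |
| Treatment periods | 2.2.1: no period 1; period 2 only after a flare | No, there is none |
| Follow-up phase | 4.1.2.1: excluded, as already in CRmin or CRoff | No |

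An entrant who flares, starts period 2 and regains CRmin there does count.

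**2. Denominator.** Section 2.4.1 has two candidate rules. The frequency rule uses the whole analysis set per treatment. The event-type rule uses the set per treatment and, as applicable, per phase or period. For a figure over the entire study there is no period to restrict to, so both give the whole Roll-over set. The SAP does write at-risk restrictions elsewhere: section 4.1.3.4 limits the flare table to those who achieved CRmin, and section 4.1.2.2 computes time to a status only where it can still be reached. The overall CRmin figure has no such sentence.

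**3. Size.** Let s be the share of the set entering in CRmin or CRoff and never flaring, and r the CRmin rate in everyone else.

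- As written: r(1 - s)
- Never-flarers left out: r
- Never-flarers counted as achievers: r(1 - s) + s

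Assume r = 60%, and take 213 participants, the approximate maximum in SAP section 1.3:

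| s | Participants | As written | Left out | Counted as achievers |
|---|---|---|---|---|
| 5% | about 11 | 57.0% | 60.0% | 62.0% |
| 16% | about 34 | 50.4% | 60.0% | 66.4% |
| 32% | about 68 | 40.8% | 60.0% | 72.8% |

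For example, 0.60 × (1 - 0.32) = 0.408, and 0.408 + 0.32 = 0.728. The drop is r × s against leaving them out (3.0 to 19.2 points) and s against counting them (5 to 32 points).

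**4. Two arms.** Assume r = 60% in both arms, 40% against 20% entering in CRmin or CRoff, and 80% of those never flaring. Then s = 0.40 × 0.80 = 32% and 0.20 × 0.80 = 16%.

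- As written: 40.8% - 50.4% = -9.6 points
- Left out: 60.0% - 60.0% = 0 points
- Counted as achievers: 72.8% - 66.4% = +6.4 points

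With equal s and equal r the difference is zero under all three. With equal s and unequal r, a real difference is only scaled by (1 - s): 70% against 60% at s = 16% becomes 58.8% - 50.4% = 8.4 points instead of 10.

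**The case against.** The strongest reply is that the treatment of these participants may already be settled. Footnote a sits on exactly the cell in question, and its wording could not be read in the copy used here, so it cannot be taken as missing from the plan. Footnote d brings the roll-over phase into Overall where applicable. Where section 4.1.2.1 does address CRmin entrants, it takes them out rather than failing them, which suggests the intent. This limits the point to what the written rules give for the pooled figure. It does not remove it. The pooled cell carries no footnote a. Footnote d does not match section 4.1.2.1, which omits the roll-over phase from the overall definition and derives only CRoff there, and the overview has no roll-over row for CRmin.

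A second reply is that the information is reported anyway: CRmin is tabulated by disease status at roll-over, and flare after CRmin in the roll-over phase has its own line. That helps a careful reader but leaves the pooled topline number unchanged.

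Third, nothing is tested, and comparisons between prior arms are purely descriptive (Protocol section 9.1.1). That stands and limits the consequence to interpretation.

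Three stronger readings are tempting and are not supported:

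- **The better 1904 arm is necessarily penalised.** This needs s to differ by arm, and the documents give no 1904 or flare rates.
- **The per-period CRmin percentages share the fault.** The event-type rule in section 2.4.1 may already supply a per-period denominator.
- **Follow-up CRoff is near zero by construction.** That requires the follow-up exclusion to remove CRmin participants from the CRoff calculation. The natural reading is respective: those on CRmin leave the CRmin calculation, those on CRoff leave the CRoff one. The can-still-reach rule in section 4.1.2.2 supports this. The wording is loose and worth tightening, but it is not shown to be an error.

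**Conclusion.** The point holds for the pooled overall CRmin percentage under the rules as written. Entrants in CRmin or CRoff who never flare cannot enter the numerator and are not removed from the denominator, so the figure is r(1 - s) rather than r. At an assumed r of 60% and s of 5% to 32%, that is a loss of 3.0 to 19.2 points. Every rate here is illustrative.

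A spurious between-arm difference follows only if s is unequal. In the example it runs from -9.6 to +6.4 points depending solely on how these participants are handled, which is why the choice should be written down. The conclusion would narrow if footnote a, once read, states a rule that carries into the pooled figure. No hypothesis test and no primary safety analysis is affected.

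**What to change.** 1. In SAP sections 4.1.2.1 and 4.1.3.1, restrict the pooled overall CRmin denominator to participants not in CRmin or CRoff at roll-over. Those who roll over with a flare after CRmin stay in.
2. Report CRmin and CRoff entrants separately on two lines: remission maintained without flare, and CRmin regained after retreatment. Do not add to the pooled denominator only those entrants who later flare, because that selects on an event after roll-over.
3. Make section 4.1.2.1 and footnotes a and d of section 4.1.3.7 say the same thing about the roll-over phase.
4. Reword the follow-up exclusion so that only participants already in CRoff are left out of the follow-up CRoff calculation.

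The cost is SAP wording and denominators in tables already planned, with no new data. The downside is that the pooled figure no longer covers the whole Roll-over set, which the table should state. It also leaves out entrants who flare, so it equals r above only if their CRmin rate matches that of the others.

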- Insufficient clinical change: the absence of DC after 3 to 4 weeks of the participant being treated at the starting baseline prednisone dose or after 3 to 4 weeks of any new incremented dose of prednisone

The recommendations of the prednisone dose escalation are:

- Stepwise escalation of daily prednisone dose by 1 or more steps according to clinical judgment in case of disease progression
- Adjustment by incrementing dosage by 1 step in case of insufficient clinical change
- Possible further escalation from the previous step by 1 or more steps, according to clinical judgment and under the same recommendation as above
- Maximum escalation to 1.5 mg/kg qd for 3 weeks

If DC is not attained after a minimum of 3 weeks of the participant receiving oral prednisone 1.5 mg/kg qd, then the participant will be considered a treatment failure and will be withdrawn from the trial.

For participants who achieve DC at the starting dose of 0.5 mg/kg qd or lower, the prednisone dose will be maintained at that starting dose qd until CR and 2 weeks thereafter, or EoC and 4 weeks thereafter, after which tapering will be initiated. For participants achieving DC with an escalated prednisone dose (ie, >0.5 mg/kg qd), that dose will be maintained until 2 weeks after achieving DC and then will be tapered (Table 4) in increments of 0.25 mg/kg every 2 weeks until the starting dose is achieved. This starting dose will be maintained until a sustained CR is achieved for 2 weeks, after which further tapering will be initiated, or prednisone tapering below 0.5 mg/kg qd may be initiated in case of sustained EoC for 4 weeks. Further tapering will be performed thereafter, as long as CR or EoC are sustained. Each new tapered prednisone dose until 20 mg/day must be maintained for 2 weeks. Then, the prednisone dose is further tapered by 2.5 mg/day per week. When 10 mg/day is reached, this dose level will be maintained for at least 8 weeks until CRmin is achieved. The prednisone dose can then be further tapered to reach CRoff according to the clinical judgment of the investigator.

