A new treatment cycle of efgartigimod PH20 SC can be initiated in eligible participants until week 44. In participants requiring a new treatment cycle of efgartigimod PH20 SC between weeks 45 and 49, the initiation will be optional and based on clinical judgment and participant consent. A new efgartigimod treatment cycle will not be permitted after week 49 to ensure a minimum of 4 weeks of efgartigimod treatment/cycle.

Except for oral prednisone, no other systemic therapies (eg, immunosuppressants, IVIg, immunoadsorption, anti-CD20 biologics) will be permitted during the trial.

Trial procedures will be performed per the SoA as detailed in Section 1.3 and Section 10.11.

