#### 4.1.3.2 TIME TO DC, CR, CRMIN AND CROFF

Time to DC, Time to CR, Time to CRmin and Time to CRoff will be descriptively presented with median times, quantiles and number and percentage of participants censored and with event, as obtained through Kaplan-Meier analysis.

The tables will be produced for PV participants and for all participants (PV+PF), also overall and by disease status at roll-over.

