#### 4.1.3.4 **PROPORTION OF PARTICIPANTS WITH FLARE AFTER CRMIN**

Frequency tabulations will be provided of the percentage (with 95% exact confidence interval) of PV participants and all participants (PV+ PF) experiencing a flare after CRmin within the roll-over phase, within each treatment period, within the follow-up phase and over the entire study. The table will be repeated by disease status at roll-over. The denominator of these tables is restricted to participants who achieved CRmin in the applicable treatment period.

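### Within-period CRmin and CRoff proportions for treatment periods 2 and later count periods begun too late to succeed as non-response, and no fixed-time estimate is planned beside them

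*SAP*

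**What the plan says.** SAP 4.1.2.1 states that the CRmin proportion "will be derived within each treatment period, within the follow-up phase and over the entire study". Its imputation rule is "CRmin never ticked: CRmin = non-response", and CRoff follows the same approach. SAP 4.1.3.1 tabulates each row with an exact 95% confidence interval.

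The exclusions in SAP 4.1.2.1 concern only people who already hold the status, for example: "For the follow-up phase, participants who start the follow-up phase on CRmin (or CRoff) will be excluded from this calculation". The general denominator rule in SAP 2.4.1 keeps everyone in the analysis set for the treatment and period. The flare table, by contrast, has its own restriction (SAP 4.1.3.4): "The denominator of these tables is restricted to participants who achieved CRmin in the applicable treatment period".

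On timing, Protocol 4.1 says "A new treatment cycle of efgartigimod PH20 SC can be initiated in eligible participants until week 44". It adds an optional window in weeks 45-49, and none after that. SAP 2.2.1 (Table 1) closes a participant's last treatment period at the week 52/EoT/ET visit. On the dose condition, Protocol 4.1 says "When 10 mg/day is reached, this dose level will be maintained for at least 8 weeks until CRmin is achieved".

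The companion time-to-event analysis (SAP 4.1.2.2) runs from the first dose of the period and censors non-achievers at the end of the period. SAP 4.1.3.2 limits its output to "median times, quantiles and number and percentage of participants censored and with event".

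**The concern.** A retreatment period can begin with less time left than CRmin takes by definition. Its outcome is then fixed before it starts, yet it enters the denominator as a non-response. Period 1 begins at roll-over with up to 52 weeks ahead, whereas a later period may have as few as 3.

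Protocol 4.2 names the effects of retreatment as something the trial will specifically evaluate, and the tables set period 1 beside periods 2 to n. A reader who compares the rows will attribute to retreatment a difference that is partly due to remaining calendar time. An exact interval shows sampling error and does not reveal this.

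SAP 4.1.2.2 does limit time to a status to participants who can still attain it. That limit covers only the time-to-event endpoints, and its example concerns a status already attained. It does not address too little remaining time.

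**Working it through.** **The plan's own figure.** Protocol 4.1 bars starts after week 49 so as to secure 4 weeks of treatment per cycle. Weekly doses at weeks 49, 50, 51 and 52 make 4 doses, so the figure reproduces as a dose count. Elapsed time to the week 52 visit is 52 - 49 = 3 weeks.

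**Bound from the definition alone.** Weeks left at start are 52 - start: week 44 leaves 8, 45 leaves 7, 46 leaves 6, 47 leaves 5, 48 leaves 4 and 49 leaves 3. CRmin needs 8 weeks at 10 mg/day or less. Starts in weeks 45-49 cannot contain that at any prednisone dose. A week 44 start could, but only with 10 mg/day or less from the first day.

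**Bound on the recommended doses.** Inputs:
- Protocol 4.1: recommended retreatment dose of 0.3 or 0.5 mg/kg; tapering 2 weeks after CR; 2 weeks per step down to 20 mg; then 2.5 mg/day per week; then 8 weeks at 10 mg.
- Table 4: these doses are 20 to 50 mg/day across the weight bands.

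Weeks from period start to CRmin = t_CR + 2 + (2 per step down to 20 mg) + 3 (17.5, 15 and 12.5 mg) + 8, where t_CR is the time to CR.

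| Starting dose | Weeks if t_CR = 0 | Latest start | Weeks if t_CR = 4 | Latest start |
|---|---|---|---|---|
| 20 mg | 2+0+3+8 = 13 | week 39 | 17 | week 35 |
| 25-35 mg | 2+2+3+8 = 15 | week 37 | 19 | week 33 |
| 40-50 mg | 2+4+3+8 = 17 | week 35 | 21 | week 31 |

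The t_CR = 0 columns are the most favourable case. Tapering may also start from sustained EoC, which per the schedule footnotes means at least 6 weeks without new lesions. Counted from period start, that route takes at least 6 + (0, 2 or 4) + 3 + 8 = 17, 19 or 21 weeks, so it does not beat the t_CR = 0 bound.

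**CRoff.** This needs at least 8 further weeks without prednisone, even if it is stopped at once after CRmin: 21, 23 or 25 weeks, with latest starts at weeks 31, 29 and 27.

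**Dilution.** Let p be the proportion responding in periods with enough time, and f the share of periods with no chance. The crude proportion is p(1 - f). The documents give neither value, so a range is shown:

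| p | f = 10% | 20% | 30% | 40% |
|---|---|---|---|---|
| 0.30 | 0.27 | 0.24 | 0.21 | 0.18 |
| 0.50 | 0.45 | 0.40 | 0.35 | 0.30 |
| 0.70 | 0.63 | 0.56 | 0.49 | 0.42 |

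**Illustration.** All inputs here are assumed: time to CRmin lognormal with median 24 weeks and SD of the log 0.35, no CRmin before 14 weeks, and starts uniform from week 5. The crude proportion is the average of F(52 - start) over the starts, where F is the distribution function of time to CRmin.
- Chance by 30 weeks: F(30) = Φ(ln(30/24)/0.35) = Φ(0.64) = 74%.
- Starts to week 49: no chance in (49 - 38)/(49 - 5) = 11/44 = 25%; crude 49%.
- Starts to week 44: no chance in (44 - 38)/(44 - 5) = 6/39 = 15%; crude 55%.
- With a 20-week median and starts to week 49: crude 58% against F(30) = 88%.

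**The case against.** The case on the other side is substantial, and most of it stands as a limit on the point.

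- **Estimand.** As a count of those who reached CRmin inside the period, the figure is right. Efficacy is secondary and descriptive, no hypothesis is tested, and the protocol's CRmin endpoint is not split by period. A reader might infer that this row is the trial's main efficacy result. The documents do not support that.
- **Other rows.** CRmin reached after week 52 counts in the follow-up and entire-study rows. A week 44 start on the 13-week path could reach it at week 57. Anyone entering period 2 from period 1 did so by flaring after CRmin, so already counts as an entire-study responder for CRmin. Only participants who entered 1905 on CRmin can lose that row through a late first cycle.
- **Kaplan-Meier.** A reader might infer that the planned output merely repeats the crude proportion. Only its event and censored percentages do so. The medians and quantiles allow for censoring at period end, and period durations are tabulated. What is missing is an estimate at a fixed time with an interval. A median may also not be estimable if short periods are common.
- **Clinical judgment.** The retreatment doses are recommendations, so the bound for starts between about weeks 35-39 and week 44 is conditional. The bound for weeks 45-49 is not, but those starts are optional and may be rare.
- **Period 1 against later periods.** A reader might attribute any shortfall in period 2 to the calendar alone. The periods also differ in population (flare after CRmin against mixed entry status), so that cannot be concluded.

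None of this supplies a rule for insufficient remaining time in the within-period proportions.

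**Conclusion.** The point holds in limited form. For periods 2 and later, the within-period CRmin and CRoff proportions include participants who could not reach the status before week 52 and score them as non-responders. For CRmin this is certain for starts in weeks 45-49. It extends to starts after about weeks 35-39, by weight band and dose, if the recommended doses and the taper from CR are followed. CRoff is affected at least 8 weeks earlier. The direction is downward relative to the chance of response with adequate follow-up, and the rows are not comparable with period 1.

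The size cannot be derived from the documents, because it depends on how many periods start late. It is zero if none do. The 49% or 55% against 74% shows what the mechanism could produce under assumed inputs. It should not be read as a forecast. This is a worthwhile, inexpensive improvement to the reporting of retreatment and does not affect the primary safety objective.

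**What to change.** Keep the crude proportion as planned. For periods 2 and later, add to SAP 4.1.2.1 and 4.1.3.1:

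1. The cumulative incidence of CRmin and of CRoff at fixed times from period start, for example 26 and 30 weeks, with 95% CI. Censor only for the administrative end at week 52. Treat treatment failure and earlier withdrawal as competing events, since censoring them would assume that these participants could still have responded. For CRoff, a flare that opens the next period also ends the current one early and should be handled the same way.
2. The number of periods by weeks remaining to week 52 at period start, so that the reader can see how many had little or no chance.
3. A footnote that the within-period proportions are not adjusted for remaining time and should not be compared with period 1.

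Limiting the crude proportion to starts before one calendar week is not an adequate substitute. The latest workable start differs by dose and weight (weeks 39, 37 or 35 at best). In the illustration, keeping only starts up to week 38 still gives about 65% against 74%.

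The cost is SAP wording and a few table rows from data already collected, with no change to treatment or visits. The drawback is that few participants will be at risk at late times, so the intervals will be wide.
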